3.3. Strata and Covariates

Randomization was stratified by HIV-1 RNA level ($\leq 100,000$ copies/mL or $> 100,000$ copies/mL) at screening.

Efficacy analyses will include HIV-1 RNA stratum ($\leq 100,000$ vs. $> 100,000$ copies/mL) at baseline as a stratification factor. The HIV-1 RNA stratum will be reclassified using baseline HIV-1 RNA level for analysis purposes.

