6.1.2. Primary Analysis of the Primary Efficacy Endpoint

The proportion of subjects with HIV-1 RNA < 50 copies/mL as determined by the US FDA-defined snapshot algorithm at Week 54 will be based on the FAS. Point estimates ($P_1 - P_2$) and its 95% confidence interval (CI) for the difference in the response rates between each of the LEN-containing regimen groups (Treatment Groups 1 to 3) and the B/F/TAF group (Treatment Group 4) will be constructed using stratum-adjusted Mantel-Haenszel (MH) proportion as described as follows {Koch 1989}, stratified by baseline HIV-1 RNA level ($\leq 100,000$ copies/mL or $> 100,000$ copies/mL):

$$P_1 - P_2 \pm Z_{(1-\alpha/2)} * SE(P_1 - P_2),$$

where

- $(P_1 - P_2) = \frac{\sum w_h d_h}{\sum w_h}$, is the stratum-adjusted MH proportion difference,

where $d_h = p_{1h} - p_{2h}$ is the difference in the response rate between of the LEN-containing regimen groups (Treatment Groups 1 to 3) and the B/F/TAF group (Treatment Group 4) in stratum h ($h=1$ to 4).

- $w_h = \frac{n_{1h} n_{2h}}{n_{1h} + n_{2h}}$, is the weight based on the harmonic mean of sample size per treatment group for each stratum where n_{1h} and n_{2h} are the sample sizes of the LEN-containing regimen groups (Treatment Groups 1 to 3) and the B/F/TAF group (Treatment Group 4) in stratum h .

- $SE(P_1 - P_2) = \sqrt{\frac{\sum w_h^2 \left[\frac{p_{1h}^* (1 - p_{1h}^*)}{n_{1h} - 1} + \frac{p_{2h}^* (1 - p_{2h}^*)}{n_{2h} - 1} \right]}{(\sum w_h)^2}}$, where $p_{1h}^* = \frac{m_{1h} + 0.5}{n_{1h} + 1}$ and

$p_{2h}^* = \frac{m_{2h} + 0.5}{n_{2h} + 1}$. m_{1h} and m_{2h} are the number of subjects with HIV-1 RNA < 50 copies/mL in the LEN-containing regimen groups (Treatment Groups 1 to 3) and the B/F/TAF group (Treatment Group 4) in stratum h .

- $\alpha = 0.05$ for this study
- $Z_{(1-\alpha/2)} = Z_{0.9750} = 1.96$ is the 97.50th percentile of the normal distribution

Note that if the computed lower confidence bound is less than -1 , the lower bound is defined as -1 . If the computed upper confidence bound is greater than 1 , the upper bound is defined as 1 .

The number and percentage of subjects with HIV-1 RNA < 50 copies/mL at Week 54 will be summarized. The associated p-values will be estimated based on the CMH test stratified by baseline HIV-1 RNA level ($\leq 100,000$ copies/mL or $> 100,000$ copies/mL).

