$$\begin{aligned} \text{Adherence(\%)} &= 100 \times \frac{\text{Total No. of pills taken}}{\text{Total No. of pills prescribed}} \\ &= 100 \times \frac{\sum \sum \text{No. of pills taken at each dispensing period for each drug}^{[1]}}{\sum \sum \text{No. of pills prescribed at each dispensing period for each drug}^{[2]}} \end{aligned}$$

13) Efficacy Analysis

- a) For categorical efficacy response (eg, Subjects with HIV-1 RNA < 50 copies/mL as determined by US FDA-defined snapshot algorithm, M=F, or M=E Analyses): the proportion difference between LEN-containing regimen groups (Treatment Groups 1 to 3) and the B/F/TAF group (Treatment Group 4) and its 95% CIs are calculated based on the MH proportion adjusted by baseline HIV-1 RNA stratum ($\leq 100,000$ vs. $> 100,000$ copies/mL) (see SAP Section 6.2 and 6.3 for details). The following SAS code will be used to compute p-value, where *brnac* is the baseline HIV-1 RNA stratum, *trtgrp* is the treatment, and *response* is the categorical efficacy response.

```
proc freq data=adeff;  
  tables brnac*trtgrp*response/cmh; /*p value from general  
  association*/  
run;
```

- b) All the ANOVA model for continuous efficacy variable (eg, CD4+): The differences in changes from baseline in \log_{10} HIV-1 RNA and CD4+ cell count between treatment groups and the associated 95% CI will be constructed using an ANOVA, including baseline HIV-1 RNA stratum *brnac*, region stratum *region*, and treatment *trtgrp* as fixed effects in the model.

```
proc glm data=adeff;  
  class brnac region trtgrp;  
  model CD4=brnac region trtgrp;  
  lsmeans trtgrp /alpha=0.05 cl pdiff;  
run;
```

14) Listing for US FDA-defined snapshot outcome:

In addition flag the values of HIV-1 RNA < 50 or ≥ 50 copies/mL for virologic outcomes.

Flag the last available HIV-1 RNA value while on treatment for the following categories:

- a) HIV-1 RNA ≥ 50 copies/mL - Discontinued Study Drug Due to Other Reasons and Last Available HIV-1 RNA ≥ 50 copies/mL
- b) No virologic Data - Discontinued Study Drug Due to Other Reasons and Last Available HIV-1 RNA < 50 copies/mL

15) Injection site reaction (ISR)

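### The code printed for the primary CMH p-value has no two-arm restriction, so run literally on four arms it gives one 3-df omnibus test, not three tests against B/F/TAF

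*SAP*

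**What the plan says.** SAP 6.1.2 defines the primary comparison as the "difference in the response rates between each of the LEN-containing regimen groups (Treatment Groups 1 to 3) and the B/F/TAF group (Treatment Group 4"). It adds: "The associated p-values will be estimated based on the CMH test stratified by baseline HIV-1 RNA level", with two levels, at or below and above 100,000 copies/mL. Protocol 8.5.1 asks for nominal two-sided CMH p-values for the same three comparisons. SAP 3.3 names one stratifier for analysis: "Efficacy analyses will include HIV-1 RNA stratum". SAP 6.5 declares no change from the protocol's efficacy analysis.

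SAP Appendix 3 item 13(a) covers categorical efficacy responses (snapshot, missing = failure and missing = excluded). It says "The following SAS code will be used to compute p-value" and prints "tables brnac*trtgrp*response/cmh; /*p value from general" association, run on `adeff`. The variable `trtgrp` is described only as the treatment. No WHERE or BY statement and no two-arm subset is shown. For details the item refers to Sections 6.2 and 6.3, although the formula is in 6.1.2.

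In the 6.1.2 formula the stratum index runs from 1 to 4, although the only factor named there has two levels.

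**The concern.** A general-association CMH statistic has (arms − 1) × (response levels − 1) degrees of freedom. With two arms and a binary response that is 1, which is the test 6.1.2 describes. With four arms it is 3, and the null hypothesis becomes equality of all four response rates. Such a p-value can be driven by differences among the LEN groups and says nothing specific about any one of them against B/F/TAF. Printed beside a pairwise difference and interval, it would be read as testing that difference.

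Two other places in the appendix favour the four-arm reading. Item 8 uses the same unrestricted CMH construction for the baseline tables, and SAP 5.1 describes that as a comparison across treatment groups. Item 13(b) runs the ANOVA on the same `adeff` and obtains pairwise contrasts through `lsmeans` with `pdiff`, which presupposes several arms in the data set. Item 13(a) has no equivalent step.

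**Working it through.** **The plan's own figure.** SAP 1.3 gives 39% power for each pair (50 v 25, 90.9% response in both groups, margin 0.12). SE = √(0.909 × 0.091 × (1/50 + 1/25)) = 0.0705. Power = Φ(0.12/0.0705 − 1.96) = Φ(−0.257) = 39.9%, or 38.8% with n − 1 denominators. The figure is reproduced. It is a pairwise calculation and does not depend on the p-value code.

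**Inputs.** Protocol 1.2.2.8 reports Week 54 responders of 47/52, 45/53, 44/52 and 23/25 for Groups 1 to 4. Counts by arm and stratum are not given, so the main check is unstratified.

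**Formula.** In one stratum the general-association statistic is Q = ((N − 1)/N) × Pearson chi-square.

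**Code as printed, four arms.**
- N = 182, with 159 responders and 23 failures.
- Expected responders are 45.43, 46.30, 45.43 and 21.84, so the deviations are 1.57, −1.30, −1.43 and 1.16.
- Σ(deviation²/n) = 0.0475 + 0.0320 + 0.0392 + 0.0538 = 0.1725.
- Dividing by (159/182)(23/182) = 0.1104 gives 1.562. Multiplying by 181/182 gives Q = 1.55 on 3 df, **p = 0.67**.

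**Tests defined in 6.1.2, two arms each.** Pearson chi-square = d² / [p̄(1 − p̄)(1/n₁ + 1/n₂)], where d is the difference in response rates and p̄ the pooled rate.

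| Pair | d | p̄(1 − p̄) | Q (1 df) | p |
|---|---|---|---|---|
| Group 1 v 4 | −0.016 | 70 × 7/77² = 0.0826 | 0.053 | **0.82** |
| Group 2 v 4 | −0.071 | 68 × 10/78² = 0.1118 | 0.755 | **0.38** |
| Group 3 v 4 | −0.074 | 67 × 10/77² = 0.1130 | 0.804 | **0.37** |

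**Sensitivity to stratification.** Protocol 1.2.2.8 puts 155 of 182 participants at or below 100,000 copies/mL, leaving 27 above. Assume these fall 8/8/8/3 across the arms.
- Three splits of the failures were tried: none above 100,000 copies/mL; 1, 1, 1 and 0 in Groups 1 to 4; and 1, 2, 2 and 1. The four-arm p runs from 0.64 to 0.68. The pairwise p-values run from 0.78 to 0.86, 0.35 to 0.42 and 0.34 to 0.40.
- Over every possible split of the failures, the smallest four-arm p is 0.086 and the smallest pairwise p is 0.10. Under this assumption no test falls below 0.05.

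**Can the two tests disagree?** Yes, in either direction.
- With invented counts of 51/52, 40/53, 47/52 and 23/25, the four-arm p is 0.003 while the pairwise p-values are 0.20, 0.09 and 0.82.
- In a 4,000-run simulation (assumed stratum sizes 43/7 per LEN group and 21/4 for B/F/TAF), with Group 1 at 70% and the others at 90.9%, the four-arm test rejects in 80% of runs and the Group 1 test in 58%.
- With Groups 2 and 3 instead at 80%, the four-arm test rejects in 36% of runs and the Group 1 test in 55%.

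**The stratum index.** One two-level factor gives two strata. Strata 3 and 4 contain nobody and contribute nothing to either sum. The Mantel-Haenszel difference and interval were computed with and without two empty strata and were identical.

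**The case against.** The best defence is that the snippet is shorthand. It has no filter for visit, endpoint or analysis set either, yet it serves several responses, and SAP 6.3.1 analyses two of them by visit. A programmer must subset the data anyway, and the contents of `adeff` are not defined. Item 13(a) itself opens with the LEN-versus-B/F/TAF difference, and 6.1.2, 6.3.1 and Protocol 8.5.1 all state the pairwise comparison. This stands in part: the intended test is not in doubt, and the four-arm result depends on what `adeff` contains when the code runs. It does not rescue the printed specification, because the arm restriction is what turns the omnibus test into the required one.

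The defence is also right about consequence. Protocol 8.5.1 calls the p-values nominal, SAP 3 makes testing descriptive, SAP 3.5 calls the trial non-confirmatory, and the primary interval does not come from this code.

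A reader might infer that the reported Week 54 comparisons rest on the wrong test. The documents do not show that. Protocol 1.2.2.8 reports no significant difference for each LEN group against B/F/TAF, which is consistent with pairwise testing, though not proof of it.

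A reader might also infer from the index 1 to 4 that the primary interval could become undefined, since the standard error divides by the control stratum size minus one and four strata would leave very small control cells. That needs a second stratification factor. A region term appears only in the ANOVA item 13(b). SAP 3.3, SAP 6.1.2, Protocol 8.5.1 and item 13(a) give the primary analysis HIV-1 RNA alone.

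**Conclusion.** The point holds for the p-value code as printed. Followed literally on a four-arm data set, item 13(a) yields one 3-df p-value (0.67 on the reported counts, unstratified) where the plan requires three 1-df p-values (0.82, 0.38 and 0.37). This assumes that `adeff` contains all four arms, which the SAP does not state but items 8 and 13(b) suggest. On the reported counts none of these unstratified p-values approaches 0.05, so the discrepancy lies in which hypothesis is tested. The primary difference, its interval and the 39% power are unaffected.

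The code and the formula each depart from 6.1.2 in one respect only: the code already uses the two-level stratifier, and the formula already compares each LEN group with B/F/TAF. The index 1 to 4 is a clerical inconsistency with no numerical effect.

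**What to change.** In SAP Appendix 3 item 13(a), restrict the data to `trtgrp in (k, 4)` and run the procedure once for each of k = 1, 2 and 3 (assuming `trtgrp` is coded by group number). State that this applies to the snapshot, missing = failure and missing = excluded responses alike. Change the item's cross-reference so that it points to Section 6.1.2 for the formula. In 6.1.2, change the stratum index to run from 1 to 2. No new analysis rule is needed.

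The cost is one line of code, one cross-reference and one index, with no new data. If the Week 54 analysis has already been run under this SAP, the clinical study report should state which CMH test produced the p-values. SAP Section 1 already provides for documenting post-finalization changes there.
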